Grade 3 or 4 ^{b, c}	
First Occurrence:
 
 • For AEs present before the next dose of MEDI-551 is to be given, delay next dose of MEDI-551 for up to 7 days until resolution to ≤ Grade 1 or baseline, and resume at 50% of current dose level. • If next dose is delayed for > 7 days due to failure of toxicity to resolve to ≤ Grade 1 or baseline, discontinue MEDI-551. • For Grade 3 infusion reaction, infusion rate may be decreased by 50% or interrupted for up to 4 hours and symptomatic care instituted as clinically indicated; steroid prophylaxis must be employed for all subsequent doses of MEDI-551. Following interruption, infusion should be resumed at 50% of original rate for remainder of infusion. For Grade 3 infusion reaction that does not respond to medical therapy (including interruption of infusion for ≤ 4 hours) or that occurs despite steroid prophylaxis, permanently discontinue MEDI-551. • For any Grade 4 infusion or allergic reaction that necessitates the use of systemic pressor agents, permanently discontinue MEDI-551. 
Second Occurrence:
 
 • Permanently discontinue MEDI-551.

See Section 6.4.1 for additional details on dose interruption and study discontinuation criteria.

^a Hematologic abnormalities equal in severity to the subject’s baseline and lymphopenia (any grade) do not require dose modification.

^b Except Grade 3 or 4 toxicities noted as exceptions to the DLT criteria (see Section 4.5.6).

^c For ≥Grade 3 hematologic toxicities other than lymphopenia, resolution to ≤ Grade 2 or subject’s baseline is required to re-initiate treatment.

Arms B, C, and D

During the DLT period, dose modification was not permitted. However, a delay in therapy due to reversible non-DLT toxicity was permitted as long as the total delay within the cycle is ≤ 7 days total. Any toxicity leading to a delay > 7 days in duration during the DLT period was considered a DLT.

Following the DLT period, subsequent cycles of MEDI-551 could be delayed or modified based on hematologic and nonhematologic toxicities observed during each subsequent cycle of treatment as described in Table 4.5.2.1-2. Both hematologic and nonhematologic toxicities were graded according to the NCI CTCAE V4.03 ([CTCAE, 2010](#)).

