4.5.6 Dose-limiting Toxicities

Dose-limiting toxicities for Arms A, B, and C are described below. This section is not relevant to Arm D.

Arm A

The period for evaluating DLTs was from the time of first administration of MEDI-551 through the first 28-day cycle. Delays of ≤ 5 days within a cycle due to reversible non-DLT toxicities were allowed during the DLT period; in that case, the DLT period was no greater than 33 days. Subjects who did not receive 2 doses (subjects enrolled under protocol Version 5.0) or 4 doses (subjects enrolled under protocol Version 4.0) of MEDI-551 during this time for reasons other than toxicity were to be replaced with another subject at the same dose level. Grading of DLTs was according to the NCI CTCAE V4.03 ([CTCAE, 2010](#)).

A DLT was defined as:

- A MEDI-551 treatment-related AE of any toxicity grade that led to an inability to receive a full cycle of MEDI-551 or
- Any Grade 3 or higher toxicity as described below that could not be reasonably ascribed to another cause, such as disease progression or accident.

During the DLT period, a delay in therapy due to a reversible non-DLT toxicity lasting ≤ 5 days total was not considered a DLT as long as the subject received the full intended dose.

Nonhematologic DLTs were any Grade 3 or higher diagnosis or laboratory finding with the following exceptions:

- Grade 3 fever that lasts \leq 24 hours with or without medical therapy and is not considered an SAE
- Transient Grade 3 rigors or chills that responds to optimum medical therapy
- Grade 3 tumor lysis syndrome that resolves to \leq Grade 2 within 72 hours after initiation of treatment
- Any Grade 3 or 4 electrolyte alteration that is reversible to \leq Grade 1 within 24 hours after it occurs
- Any Grade 3 liver function test elevation that resolves to \leq Grade 1 within 24 hours after it occurs

Grade 3 or higher hematologic toxicities were considered DLTs with the following exceptions:

- \geq Grade 3 lymphopenia or leukopenia in the absence of neutropenia
- \leq Grade 4 neutropenia in the absence of fever that resolves within 5 days
- \leq Grade 4 thrombocytopenia that resolves within 5 days
- \leq Grade 4 anemia in a subject who was transfusion dependent at study entry, or had a history of hemolysis

Arms B and C

The period for evaluating DLTs was from the time of first administration of MEDI-551 through the first 28-day cycle. Grading of DLTs was according to the NCI CTCAE V4.03 ([CTCAE, 2010](#)).

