A DLT was defined as:

- A MEDI-551 (or rituximab for Arm C) treatment-related AE of any toxicity grade that led to an inability to receive a full cycle of MEDI-551 (or rituximab for Arm C).
- **NOTE:** During the DLT period, a delay in therapy due to a reversible non-DLT toxicity lasting \leq 7 days total would not be considered a DLT as long as the subject received the full intended dose.

Nonhematologic DLTs were any Grade 3 or higher MEDI-551 (or rituximab for Arm C) treatment-related toxicity not attributable to another cause with the following exceptions:

- Grade 3 fever that lasted \leq 24 hours with or without medical therapy and is not considered an SAE
- Grade 3 rigors or chills lasting $<$ 6 hours that respond to optimum medical therapy

- Grade 3 IRR (first occurrence and in the absence of steroid prophylaxis) that resolves within 6 hours with appropriate clinical management
- Grade 3 tumor lysis syndrome that resolves to \leq Grade 2 within 72 hours after initiation of treatment
- Any Grade 3 electrolyte alteration that is reversible to \leq Grade 1 within 72 hours after it occurs
- Any Grade 3 liver function test elevation up to $8 \times$ ULN and total bilirubin up to $5 \times$ ULN that resolves to \leq Grade 1 within 72 hours after it occurs. Any liver function test elevation $> 8 \times$ ULN or total bilirubin elevation $> 5 \times$ ULN that is attributed to investigational product requires discontinuation of investigational product.

Hematologic DLTs were any Grade 3 or higher MEDI-551 (or rituximab for Arm C) treatment-related toxicity not attributable to another cause, with the following exceptions:

- Grade 3 or 4 neutropenia in the absence of fever or infection that resolves to Grade 2 within 7 days
- Grade 3 or 4 thrombocytopenia that resolves to Grade 2 within 7 days and does not require a transfusion
- Grade 3 anemia that resolves to Grade 2 within 7 days and does not require a transfusion
- Grade 3 or 4 lymphopenia

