6.4.1 Interruption or Permanent Discontinuation of Study Dosing in Individual Subjects

Dosing of MEDI-551 may be interrupted for up to 4 hours in subjects experiencing Grade 2 or 3 infusion reactions as described in Section 4.5.2.

An individual subject will not receive any further investigational product (i.e., permanent discontinuation) if any of the following occur in the subject in question:

1. Withdrawal of consent;
2. Allergic reactions \geq Grade 2 or any allergic reaction that necessitates the use of systemic pressors.
 - Grade 3 infusion reactions that do not respond to medical therapy (including interruption of infusion for \leq 4 hours) or that occur despite steroid prophylaxis. Any Grade 4 infusion reaction or any infusion reaction that necessitates the use of systemic pressors.
3. Grade 3 infusion reactions that respond to medical therapy or slowing the infusion rate and that are of limited duration will not necessitate dose interruption or discontinuation.
4. Pregnancy;
5. DLT (see Section 4.5.6 for definition of DLTs). The Medical Monitor may decide that certain events meeting the criteria for DLT are controllable and that retreatment is considered safe.
 - a. Subjects whose DLT resolves to \leq Grade 1 or baseline within 7 days can be retreated during the DLT period at one dose level below the subject's prior dose for all arms of the study except the first dose-escalation cohort of Arms B and C.
 - b. Subjects with toxicities considered DLTs that persist beyond 7 days will not be retreated for Arm A only.
 - c. Recurrence of the DLT following retreatment will necessitate permanent discontinuation of treatment with MEDI-551 for Arm A only.
6. Delay in administration of MEDI-551 for more than 21 days for reason of toxicity within any 3 consecutive cycles for Arm A or delay in cycles as dictated in Section 6.4.1 for Arms B, C, and D;
7. Recurrence of any \geq Grade 3 toxicity not attributable to other causes unless otherwise specified in Section 6.4.1;
8. Documentation of disease progression;
9. Any event which, in the opinion of the investigator, contraindicates further dosing such as intercurrent illnesses, significant drug toxicities or complications if judged by the investigator to be in the best interest of the subject;
10. Subject non-compliance;

11. Treatment with another investigational agent;
12. Initiation of alternative anticancer therapy;

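### Arms B and C: the half-dose resumption rule in Table 4.5.2.1-2 conflicts with the hepatic stop in 4.5.6, and 6.4.1 does not repeat that stop

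*Protocol*

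**What the plan says.** Four places in the protocol bear on this.

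- **4.5.6, Arms B and C.** The last bullet of the nonhematologic DLT exceptions excuses a Grade 3 liver test up to 8 × ULN, with bilirubin up to 5 × ULN, if it resolves within 72 hours. The same bullet then says that an elevation above either limit "that is attributed to investigational product requires discontinuation of investigational product". It names no cycle, no exception for quick recovery and no override.
- **4.5.2.1 and Table 4.5.2.1-2, Arms B, C and D.** "Following the DLT period, subsequent cycles of MEDI-551 could be delayed or modified" according to the table. In the Grade 3 or 4 nonhematologic row, a first event leads to a delay of up to 7 days and resumption at half the current dose. If it has not settled by then, dosing stops permanently. Footnote a exempts toxicities listed in 4.5.6 as exceptions to the DLT criteria. The note under the table sends the reader to 6.4.1 for discontinuation criteria.
- **6.4.1.** None of the 13 items names a hepatic threshold. Item 5 stops dosing for a DLT, then adds: "The Medical Monitor may decide that certain events meeting the criteria for DLT are controllable and that retreatment is considered safe". Under item 5a, a subject whose DLT resolves within 7 days "can be retreated during the DLT period at one dose level below" the prior dose, except in the first escalation cohorts of Arms B and C. The bar in item 5b on retreating longer-lasting DLTs reads "will not be retreated for Arm A only".
- **6.4.2.** It names 6.4.1 as the section that holds withdrawal criteria for individual subjects.

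**The concern.** A site that sees a drug-attributed elevation above the limits after Cycle 1 has two instructions. Section 4.5.6 says stop. The table says wait up to 7 days and resume at half dose. The section that a site would open to settle the question, 6.4.1, is silent on the hepatic limits. A site that follows the table would redose a subject whom 4.5.6 says must come off drug. What is at stake is the safety of the few subjects still being dosed. No estimate, test or analysis population is touched.

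**Working it through.** The protocol gives no figure to reproduce. The check compares the rules for one event and then counts whom they can reach.

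**The event.** ALT 9 × ULN, attributed to MEDI-551, in an Arm C subject on 12 mg/kg. It is the first such event, is present when the next dose is due, and settles in 5 days.

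**Grade.** The 4.5.6 bullet treats 8 × and 5 × ULN as lying within Grade 3. Anything higher is therefore Grade 3 or above and falls in the Grade 3 or 4 row of the table.

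**After Cycle 1**
- 4.5.6: 9 × exceeds 8 ×, so the subject stops.
- Table row: settled within 7 days, so resume at 50% × 12 = 6 mg/kg.
- Footnote a: the DLT exception ends at 8 × (bilirubin 5 ×). At 9 × the event is not an exception, so the footnote does not take it out of the row.
- 6.4.1: item 5 concerns DLTs, and "The period for evaluating DLTs was from the time of first administration of MEDI-551 through the first 28-day cycle", so it no longer applies. Item 6 acts only on prolonged delay. Item 7 acts only on recurrence of a "Grade 3 toxicity not attributable to other causes unless otherwise specified in Section 6.4.1" event of that grade or higher. Item 9 covers "Any event which, in the opinion of the investigator, contraindicates further dosing", which is a judgement. Of 13 items, 0 make this first event a mandatory stop.

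If the event lasted more than 7 days, or recurred, the table would stop dosing anyway. The conflict is therefore confined to first events that settle within 7 days.

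**In Cycle 1 (historical)**
- Above 8 × ULN the event is a DLT, because it lies outside the excepted range. Section 4.5.6 requires a stop. Items 5 and 5a would have allowed retreatment one level down, at 8 mg/kg.

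**Reach**
- Still on treatment at 19Jan2017 (3.1): 9 subjects, each with at least 1 year of treatment, arms not given. In Arms B and C: 0 to 9.
- Historical, from the escalation cohorts in 7.5: Arm B 3 + 3 + 1 = 7 and Arm C 3 + 3 = 6, total 13. Removing the first cohorts, 3 + 3 = 6, leaves 13 − 6 = 7 (4 in Arm B, 3 in Arm C).
- That 7 is not firm. Section 7.5 also says 16 Arm C subjects received 12 mg/kg, and the abstract says Arm C stopped before dose expansion. If the DLT rules applied to all 16, the figure is 4 + 16 = 20.

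**The case against.** The strongest reply is that footnote a already carries 4.5.6 into dosing after Cycle 1, and sends the reader to the very bullet that contains the stop. Sections 4.5.3 and 6.4.3 also cite 4.5.6 when they discuss permanent discontinuation after infusion reactions, so a stop need not appear in 6.4.1 to bind. Both observations are correct. They rule out the inference that the hepatic stop has no force because 6.4.1 omits it. They do not remove the conflict: the footnote exempts the exceptions, and an elevation above the limits is not one, so the row still says resume at half dose.

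A second reply is that item 5 only permits retreatment of certain DLTs and compels nobody to redose. A site could satisfy both texts by stopping. That holds for item 5, and a reader should not infer that 6.4.1 overrides 4.5.6; the protocol states no order of precedence. The table row is different, because it directs resumption.

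A third reply is that the stop sits in a section about DLTs and may be meant for Cycle 1 only. The sentence carries no such limit, but its position makes that reading possible. On that reading the table conflict disappears and only the historical Cycle 1 part is left. In addition, 4.5.6 does not use the word permanent.

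A reader might also infer that a liver stop was missed. The document does not support that. Section 1.4, at its 31Mar2015 data cutoff, reports two DLTs in this study, both infusion-related reactions.

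**Conclusion.** The conflict holds as a minor inconsistency in a safety rule. For Arms B and C, a first drug-attributed liver test above 8 × ULN or total bilirubin above 5 × ULN that settles within 7 days must stop under 4.5.6 and resumes at half dose under Table 4.5.2.1-2. This rests on taking the 4.5.6 sentence as written, without a time limit, and its discontinuation as lasting.

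The live reach is 0 to 9 subjects and may be none. The Cycle 1 part can no longer affect anyone, since enrollment closed on 30Sep2015 and everyone still dosing is well past the DLT period. A figure of at most 7 subjects exposed to it should not be relied on. Priority is low, and no effect on the efficacy analysis is claimed.

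**What to change.** Make the same addition in two places: the Grade 3 or 4 nonhematologic row of Table 4.5.2.1-2, and a separate new item in 6.4.1. Suggested wording: *For Arms B and C, a liver test > 8 × ULN or total bilirubin > 5 × ULN attributed to investigational product requires permanent discontinuation in any cycle; items 5 and 5a and resumption at 50% do not apply.* The sponsor should confirm that permanent and in any cycle are what 4.5.6 was meant to say.

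A clarification letter or a line in the next amendment is enough. No new tests are needed: the Version 13.0 schedule already has serum chemistry on Day 1 of every cycle, and 5.3.2 already requires AST, ALT and total bilirubin to be assessed together. The clinical cost is that a subject with a quickly reversible elevation can no longer resume at a reduced dose.

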The following AEs were exceptions to the dose modification and stopping rules described in Table 4.5.2.1-2 and required NO modification of MEDI-551 dosing: lymphopenia (any grade) or hypogammaglobulinemia. Dose modification for Grade 2, 3, or 4 AEs occurred as described in Table 4.5.2.1-2. Laboratory changes within a cycle did not require prompt dose modification or delay unless clinically indicated in the investigator’s opinion. Adverse events

for which a cause other than MEDI-551 could be clearly attributed (such as an accident) did not result in a dose delay or reduction. If more than one dose reduction was needed for the same toxicity, the subject was required to permanently discontinue treatment.

For subjects in the dose-escalation portion of Arms B and C, if the start of Cycle 2 was delayed for toxicity-related reasons beyond 7 days, the subject was considered to have had a DLT and was required to resume dosing at a dose level below which they were enrolled. If the subject was unable to recover from toxicity within 7 days despite the dose modification indicated in [Table 4.5.2.1-2](#), they were required to permanently discontinue treatment. The start of Cycle 3 and beyond was allowed to be delayed by up to 7 days to permit resolution of toxicity or for logistical reasons. If a subject delayed 2 consecutive cycles by >7 days each, they were to be withdrawn from therapy even if delays are due to different toxicities.

For all subjects in the dose-expansion portion of Arms B and C, and for all subjects enrolled in Arm D, any cycle could be delayed by 7 days to permit resolution of toxicity or for logistical reasons. For a given subject, a single cycle was allowed to be delayed by up to 28 days to permit recovery from toxicity. Upon recovery of toxicity, dose modification was required to be performed according to the guidelines provided in [Table 4.5.2.1-2](#). If a cycle was delayed by > 28 days, the subject was required to permanently discontinue treatment. If a subject had received 1 dose reduction and a subsequent cycle was delayed by > 7 days to permit recovery from toxicity, the subject was required to permanently discontinue treatment. If 2 consecutive cycles were delayed by 7 days each, the subject was required to permanently discontinue therapy even if delays are due to different toxicities.

Table 4.5.2.1-2 MEDI-551 Dose Modifications for Nonhematologic and Hematologic Toxicity in Arms B, C, and D

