Grade 3 or 4 ^{a,b}	
First Occurrence:
 
 • For AEs present before the next dose of MEDI-551 is to be given, delay next dose of MEDI-551 for up to 7 days until resolution to ≤ Grade 1 or baseline, and resume at 50% of current dose level. • If next dose is delayed for > 7 days due to failure of toxicity to resolve to ≤ Grade 1 or baseline, permanently discontinue MEDI-551. • For Grade 3 infusion reaction, infusion must be stopped for up to 4 hours until the subject recovers. An additional dose of steroids will be given and the infusion may resume but the infusion rate must be decreased by 50% for remainder of infusion. For Grade 3 infusion reaction that does not respond to medical therapy (including interruption of infusion for ≤ 4 hours) or that occurs despite steroid prophylaxis, discontinue MEDI-551. • For any Grade 4 infusion or allergic reaction that necessitates the use of systemic pressor agents, permanently discontinue MEDI-551. 
Second Occurrence:
 
 • For AEs present before the next dose of MEDI-551 is to be given, permanently discontinue MEDI-551.
Hematologic Toxicity ^{c,d}	
Grade 1 or 2	None
Grade 3 ^{a,b}	
First Occurrence:
 
 • Delay dose by up to 7 days until resolution to ≤ Grade 2 and resume at current dose level. If subject does not recover to ≤ Grade 2 within that time, permanently discontinue MEDI-551. 
Second Occurrence:
 
 • Delay dose by up to 7 days until resolution to ≤ Grade 2 and decrease dose by 50%. If subject does not recover to ≤ Grade 2 within that time, permanently discontinue MEDI-551. 
Third Occurrence:
 
 • Permanently discontinue MEDI-551.
Grade 4 ^{a,b}	
First Occurrence:
 
 • Delay dose by up to 7 days until resolution to ≤ Grade 2 and decrease dose by 50%. If subject does not recover to ≤ Grade 2 within that time, permanently discontinue MEDI-551. 
Second Occurrence:
 
 • Permanently discontinue MEDI-551.

See Section 6.4.1 for additional details on dose interruption and study discontinuation criteria.

- ^a Except Grade 3 or 4 toxicities noted as exceptions to the Dose Limiting Toxicity (DLT) criteria (see Section 4.5.6).

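### Footnote a of Table 4.5.2.1-2 takes its exemptions from Section 4.5.6, which excludes Arm D, so the dose rule for short uncomplicated Grade 4 cytopenias in Arm D is unsettled; in Arms B and C the footnote also conflicts with the 4.5.2.1 list and with 6.4.1 item 7

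*Protocol*

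**What the plan says.** Five places in the protocol bear on this.

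- **Table 4.5.2.1-2, hematologic rows (Arms B, C and D).** A first Grade 3 event: "Delay dose by up to 7 days until resolution to ≤ Grade 2 and resume at current dose level". A second Grade 3 event, or a first Grade 4 event: "Delay dose by up to 7 days until resolution to ≤ Grade 2 and decrease dose by 50" percent. In each case MEDI-551 is stopped for good if recovery does not come in that time. A third Grade 3 or a second Grade 4 event also stops it.
- **Footnote a, marked on both rows.** "Except Grade 3 or 4 toxicities noted as exceptions to the Dose Limiting Toxicity (DLT) criteria", with a pointer to Section 4.5.6.
- **Section 4.5.6.** Its scope sentence reads: "This section is not relevant to Arm D". For Arms B and C its hematologic exceptions include "Grade 3 or 4 neutropenia in the absence of fever or infection that resolves to Grade 2 within 7 days", and Grade 3 or 4 thrombocytopenia with the same recovery limit and no transfusion. Anemia is excepted only at Grade 3.
- **Section 4.5.2.1, text for Arms B, C and D.** The events that "required NO modification of MEDI-551 dosing: lymphopenia (any grade) or hypogammaglobulinemia" are the only ones named. Grade 2 to 4 adverse events are then referred to the table.
- **Section 6.4.1, item 7.** Dosing ends permanently when a toxicity of Grade 3 or higher, not due to another cause, recurs. The item's escape clause points to Section 6.4.1, the section it stands in.

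**The concern.** The table covers three arms, but the list of exemptions it borrows is written for two of them and expressly set aside for the third. In Arm D a site can argue that the footnote applies, because the table's title includes Arm D. It can equally argue that the footnote has no content there, because 4.5.6 says so. One reading leaves the dose unchanged and the other halves it.

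In Arms B and C the footnote has content, but two other passages do not fit it. The 4.5.2.1 list is shorter than the footnote's, and 6.4.1 item 7 is stricter than both the footnote and the Grade 3 row on recurrence. No passage says which text prevails.

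Subject safety is at stake, and so is the interpretation of response by dose. Clinical activity is a primary endpoint in Arms B, C and D (Section 7.3.1), and the dose actually received at a nominal 12 mg/kg could depend on which line a site followed.

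**Working it through.** The plan has no figure to reproduce here, so the rules are set side by side for one kind of event.

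**Assumed case.** Neutropenia without fever or infection, or thrombocytopenia without transfusion. It begins at a due dose, is worse than the subject's baseline grade, and recovers to Grade 2 after 5 days of delay. The condition that it be present at a due dose matters: 4.5.2.1 says laboratory changes within a cycle need no prompt modification or delay unless clinically indicated.

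| Event | Row alone | Row with footnote a | 6.4.1 item 7 |
|---|---|---|---|
| Grade 3, first | full dose | no change | does not apply |
| Grade 3, second | half dose | no change | stop |
| Grade 3, third | stop | no change | stop |
| Grade 4, first | half dose | no change | does not apply |
| Grade 4, second | stop | no change | stop |

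**Arm D.** If 4.5.6 does not apply, the first column governs. If the footnote imports the list regardless, the second does. For a first Grade 4 event the answer is half dose or no change.

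**Arms B and C.** The footnote is attached to the rows, so the second column is a coherent reading of the table. The 4.5.2.1 list does not name these events, and the fourth column contradicts the second on every recurrence. It also contradicts the Grade 3 row on a second event.

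**How much of the half-dose row the exemption removes.** The row counts days of dose delay, whereas 4.5.6 counts time to resolution.

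- If the event starts at the due dose, the two clocks agree. Recovery on any of days 1 to 7 meets both conditions, so the exemption removes the first-event Grade 4 half-dose outcome on 7 of 7 days.
- If the event began 5 days before the due dose and clears after 5 days of delay, it has lasted 5 + 5 = 10 days. On a clock running from onset, 10 > 7, so it is not exempt. The delay of 5 days is within 7, so the half-dose row applies.
- Febrile or infected Grade 4 neutropenia, transfused Grade 4 thrombocytopenia and Grade 4 anemia stay in the row in any case.

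The exemption therefore takes out most, but not all, short uncomplicated events.

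**Subjects.** Arm B 7 + Arm C 19 + Arm D 16 = 42. Arms B and C together hold 7 + 19 = 26.

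**The case against.** A row with an exception marked on it is not self-contradictory. The 4.5.2.1 text refers Grade 2 to 4 events to the table, footnotes included, and its short list does not claim to be exhaustive. The scope sentence of 4.5.6 may mean only that Arm D has no dose escalation, leaving its list usable for other purposes. For Arms B and C this largely stands as regards table and footnote. It does not deal with 6.4.1 item 7, which defers to neither. For Arm D it is a plausible guess at intent that the text does not confirm.

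Three stronger readings are tempting, and the documents do not support them:

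- **That the exemption wholly cancels the 50% cut.** The two clocks differ, and complicated events and Grade 4 anemia remain in the row.
- **That Arm A is free of the problem because its exemption runs 5 days against a 7-day row.** Arm A neutropenia without fever, or thrombocytopenia, that resolves within 5 days meets the same overlap between row and footnote.
- **That the table, its footnote and 4.5.6 alone give full dose, half dose or stop for one event.** All three outcomes arise only for a second Grade 3 event, and only when 6.4.1 item 7 is added.

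On impact, the objection is right that little is shown. Section 1.4 places neutropenia among related events in at least 5% of subjects, but without grade and pooled over 111 subjects including Arm A. Nothing shows that sites read the lines differently.

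**Conclusion.** The point holds in limited form. For Arm D (16 subjects) the protocol does not determine whether a short uncomplicated Grade 4 neutropenia or untransfused thrombocytopenia present at a due dose is exempt or leads to a 50% reduction. For Arms B and C the footnote can be read as a carve-out, but the 4.5.2.1 list does not match it. Section 6.4.1 item 7 also gives a different outcome on recurrence: a second uncomplicated Grade 3 event yields no change, half dose or discontinuation depending on the passage followed.

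This rests on the wording alone and on events being present at a due dose. The number of subjects affected cannot be estimated, because no Grade 3 or 4 cytopenia rate is given for these arms. The forward reach is small: enrollment closed on 30 September 2015, and the arms of the nine subjects on treatment at 19 January 2017 are not stated. An effect on observed response in Arms C or D might be inferred, but nothing in the protocol demonstrates one. The correction is still worthwhile, since it concerns dosing and costs little.

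**What to change.** Reconcile footnote a, the hematologic rows of Table 4.5.2.1-2, the 4.5.2.1 list of events needing no modification, the scope sentence of 4.5.6 and item 7 of 6.4.1. State once, in 4.5.2.1:

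- which Grade 3 or 4 events are exempt from dose modification;
- whether the exemption holds on recurrence;
- whether it applies to Arm D.

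Replace the self-reference in 6.4.1 item 7 with a pointer to wherever its exceptions are actually given. This review does not choose among the dosing rules. The cost is wording in two sections and a footnote, with no new data. Whether to list subjects dosed under the conflicting lines can be left to the analysis plan.
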